1.3.3 SoA for 2-Dose Panels (Day 1, Day 169)

2-dose Day 1, Day 169-Panels F and K-L														
	Screening	Study Day											Post-Study	Notes
Scheduled Hour, Day, Week, etc.	Screening -28 to -1	Day 1 Pre-dose	1	2 ^a	8±1	15±1	29±3	85±3	169±3	170 ^a	197±3	365±7	534±14	Section 8.11.5 Details on variance in procedure collection times
Administrative Procedures														
Informed Consent	X													Section 8.1.1.1
Informed Consent for Future Biomedical Research	X													Section 8.1.1.2
Demographics	X													
Inclusion/Exclusion Criteria	X	X							X					Section 5.0
Participant ID Card	X													Section 8.1.3
Medical History & Vaccination History	X													Section 8.1.4
Prior/Concomitant Medication Review	X	X	X	X	X	X	X	X	X	X	X	X	X	Sections 6.6, 8.1.5 Including Non-study Vaccination Review
Assignment of Screening Numbers	X													Section 8.1.6
Assignment of Randomization Number		X												Sections 5.5 and 8.1.7
COVID-19 Symptoms Training		X			X	X	X	X		X	X			Section 8.3.7
V591/Placebo Administration			X						X					Section 8.1.8
Clinical Procedures/ Safety Assessment														
Full physical examination	X	X											X	Section 8.3.1.1
Symptoms driven physical exam			X		X	X	X	X	X		X			Section 8.3.1.2 Only to be conducted if participant symptoms warrant an exam or at investigator's discretion
Targeted physical examination of injection site			X		X	X			X					Section 8.3.1.3 At ~ 1 hour postdose on Day 1 and Day 169

2-dose Day 1, Day 169-Panels F and K-L															
	Screening	Study Day											Post-Study	Notes	
Scheduled Hour, Day, Week, etc.	Screening -28 to -1	Day 1 Pre-dose	1	2 ^a	8±1	15±1	29±3	85±3	169±3	170 ^a	197±3	365±7	534±14		
Height	X														Section 8.3.1.4
Weight	X								X				X		Section 8.3.1.4
Semi-recumbent Vital Signs (Blood Pressure [BP] and Heart Rate [HR] and Respiratory Rate [RR])	X	X	X		X	X	X	X	X		X	X	X		Section 8.3.2 Day 1 predose measurements will be done within ~ 3 hours of dosing. Day 1 and Day 169: Postdose measurements will be taken ~ 1 hour after vaccination.
Body Temperature	X	X	X	X	X	X	X	X	X	X	X	X	X		Section 8.3.2.2 (temperature) and Section 8.3.5 (VRC) Days 1 to 14 and Days 169 to 182 will be done by participant and recorded on the VRC. All other measurements will be done by clinic staff.
12-lead ECG	X	X													Section 8.3.3 Day 1 predose ECG will be done within 24 hours of dosing.
Distribute Paper Vaccination Report Card (VRC)			X						X						

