Serum Collection for Neutralizing Antibodies by PNA		X				X	X	X	X		X	X	X	Leftover main study serum samples to be stored for FBR
Serum Collection for Total Anti-spike IgG and Total Anti-N IgG Antibodies by ELISA		X				X	X	X	X		X	X	X	Leftover main study serum samples to be stored for FBR
PBMC collection for Immunological Assessments		X									X			Leftover main study PBMC samples to be stored for FBR
Biomarkers														
Blood (DNA) for Future Biomedical Research		X												Section 8.9 Collect from enrolled participants only.
AE=adverse event; β-hCG=beta human chorionic gonadotropin; BDS=blood drug screen; BP=blood pressure; DNA=deoxyribonucleic acid; ECG=electrocardiogram; ECI=event(s) of clinical interest; ELISA=enzyme-linked immunosorbent assay; FBR=future biomedical research; FSH=follicle stimulating hormone; HIV=human immunodeficiency virus; HR=heart rate; ID=identification; IgG=immunoglobulin G; MAAE= Medically Attended Adverse Event; PBMC=peripheral blood mononuclear cells; PCR=polymerase chain reaction; PNA=Pseudo-virus Neutralization Assay; RR=respiratory rate; SAE=serious adverse event; SARS-CoV-2=Severe Acute Respiratory Syndrome Coronavirus (novel); SOP=standard operating procedure; UDS=Urine Drug Screen; VRC=vaccine report card; WOCBP=women of childbearing potential; WONCBP=women of nonchildbearing potential														
a. Safety calls on Days 2 and 170 must occur on the day after the Day 1 and Day 169 visits, respectively, approximately 18 to 30 hours postdose.														

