3 HYPOTHESES, OBJECTIVES, AND ENDPOINTS

Healthy male participants and female participants between the ages of 18-55 years (inclusive) of age in Parts 1 and 2A (younger adults) and > 55 years of age in Part 2B (older adults)

Objectives	Endpoints
Primary	
To assess the safety and tolerability of V591 compared with placebo	
Solicited injection site adverse events from Day 1 through Day 5 after any study intervention
 
Solicited systemic adverse events from Day 1 through Day 14 after any study intervention
 
Unsolicited adverse events from Day 1 through Day 28 after any study intervention
 
SAEs from Day 1 throughout the duration of study
 
Medical attended AEs (MAAEs) collected from Day 1 throughout the duration of study

Secondary	
To compare the humoral immunogenicity of V591 with placebo at Day 29 (all panels) and Day 85 (Panels A, B, I, and J) or Day 197 (Panels K and L)	
Anti-SARS-CoV-2 spike serum neutralizing antibody (nAb) responses, as measured by Pseudo-virus Neutralization Assay (PNA)
 
Anti-SARS-CoV-2 spike Immunoglobulin G (IgG) responses, as measured by ELISA

To evaluate the humoral immunogenicity of V591 at all timepoints with serum collection	
Anti-SARS-CoV-2 spike serum nAb responses, as measured by Pseudo-virus Neutralization Assay (PNA)
 
Anti-SARS-CoV-2 spike IgG responses, as measured by ELISA

Tertiary/Exploratory	
To evaluate the immune response to of V591, including cell-mediated immunity	
PBMCs stimulated with SARS-CoV-2 Spike peptides for characterization of cell mediated immunity and serum to characterize the immune response to V591

[figure not shown]
Objectives	Endpoints
To characterize SARS-CoV-2 seroconversion rates among participants	Anti-SARS-CoV-2 N-protein IgG responses, as measured by immunoassay
To document confirmed diagnoses of SARS-CoV-2 infection among study participants	Laboratory confirmed diagnosis of SARS-CoV-2 infection reported as an ECI
To document study participants' exposures to confirmed SARS-CoV-2 cases	Known exposure to a confirmed case of active SARS-CoV-2 reported as an ECI

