8.1.8.1 Timing of Dose Administration

The first dose of study vaccine will be administered on Day 1, which should be the day of randomization. For 2-dose Day 1, Day 57 panels, the second vaccination will be administered on Day 57. For 2-dose Day 1, Day 169 panels, the second vaccination will be administered on Day 169. Vaccinations may be administered in the morning and without regard to timing of meals.

Each participant's body temperature must be taken before vaccine administration. After randomization, the dosing for individuals who present with fever (oral $\geq 100.4^{\circ}\text{F}$ [$\geq 38.0^{\circ}\text{C}$]) may be rescheduled when the fever has resolved. In addition, the second vaccination will be administered after predose procedures are executed as per SOA and adherence to study restrictions has been confirmed.

The predose collection of blood samples must be performed before vaccine administration.

As described in section 4.2.6, all participants will be observed for at least 8 hours for sentinel panels (Panel A and B) after the first and the second vaccination. At a minimum the first 5 participants enrolled in Panel E that will be conservatively monitored for at least 8 hours after their vaccination as well. The rest of the participants in the study will be monitored for at least 1 hour after vaccination.

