9.6.2 Statistical Methods for Immunogenicity Analyses

This section describes the statistical methods that address the secondary immunogenicity objectives. Methods related to exploratory objectives will be further described in the supplemental statistical analysis plan.

The geometric mean ratios and 95% CIs of the anti-SARS-CoV-2 spike serum nAb GMTs will be calculated using a cLDA method proposed by Liang and Zeger (2000) [Liang, K-Y and Zeger, S. L. 2000]. In this model, the response vector consists of the log-transformed prevaccination and postvaccination antibody titers. The repeated measures model will include terms for time, the interaction of time-by-vaccination group (with a restriction of the same baseline mean across groups). The treatment difference in terms of a geometric mean ratio at a given postvaccination time point will be estimated and tested from this model. The term for time will be treated as a categorical variable. An unstructured covariance matrix will be used to model the correlation among repeated measurements. This model allows the inclusion of participants who are missing either the baseline or postbaseline measurements, thereby increasing efficiency.

The observed nAb GMTs at each timepoint with serum collection and GMFRs from prevaccination to postvaccination will be performed within each vaccination group separately. Descriptive statistics with point estimates and within-group 95% CIs will be provided. The point estimates will be calculated by exponentiating the estimates of the mean of the natural log values and the within-group CIs will be derived by exponentiating the bounds of CIs of the mean of the natural log values based on the t-distribution.

A similar statistical approach will be used to evaluate the anti-SARS-CoV-2 spike serum IgG responses.

For responses smaller than the lower limit of quantitation (LLOQ), half of the LLOQ will be used for analysis when calculating the nAb GMTs and IgG GMCs.

A detailed analysis strategy for key immunogenicity endpoints is listed in [Table 10](#).

Table 10 Analysis Strategy for Immunogenicity Variables

Endpoint/Variable (Description, Time Point)	Primary vs. Supportive Approach ^a	Statistical Method	Analysis Population	Missing Data Approach
Secondary Endpoint				
nAb GMT ratio and IgG GMC ratio at Day 29 (all panels) and Day 85 (2-dose panels only)	P/S	cLDA model ^b (estimate and 95% CI)	PP/FAS	Model-based

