9.7 Interim Analyses

Up to two interim analyses may be performed on safety and immunogenicity data through at least Day 29. In order to trigger the first interim analysis at least 75% of study participants per Panel in at least 6 Panels must have completed their Day 29 visit. In order to trigger the second interim analysis at least 75% of study participants per Panel in at least 10 Panels must have completed their Day 29 visit.

An interim analysis may be performed on safety and immunogenicity data through at least Day 85 for Panels A, B, I, and J. To trigger this interim analysis at least 75% of these Panel's participants must have completed their Day 85 visit. A minimum percentage of participants from other study Panels is not required for this interim analysis, though all available data will be included.

An interim analysis may be performed on safety and immunogenicity data through at least Day 197 for Panels K and L. To trigger this interim analysis at least 75% of these Panel's participants must have completed their Day 197 visit. A minimum percentage of participants from other study Panels is not required for this interim analysis, though all available data will be included.

These interim immunogenicity analyses will include all available nAb PNA and IgG ELISA data.

For this early phase study, an internal statistician, statistical programmer, and modelers assigned to the protocol will be unblinded throughout the duration of the study to facilitate the interim reviews and analyses of the safety and immunogenicity data. Analyses of immunogenicity data may also be conducted at the discretion of the sponsor when data are available.

Results of the interim analysis will be provided to the unblinded siDMC. The siDMC will make a recommendation for further clinical development. Group summaries will be reviewed by the Sponsor's study team. Sponsor's study team (except for the unblinded statistician and programmer) will be blinded to the V591 treatment information at the participant level.

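### Table 10 puts the ratio to placebo at Day 85 for every two-dose panel and plans none at Day 197, contrary to Section 3; in Panels F, K and L Day 85 is 84 days before the second dose

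*Combined protocol and SAP*

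**What the plan says.** - Table 10, Section 9.6.2, gives the time points for the cLDA ratio to placebo: "nAb GMT ratio and IgG GMC ratio at Day 29 (all panels) and Day 85 (2-dose panels only"). Day 197 does not appear in that row.
- The secondary objective in Section 3, repeated in the synopsis, compares V591 with placebo at Day 29 in all panels, then at "Day 85 (Panels A, B, I, and J) or Day 197 (Panels K and L"). Panel F is named for neither later day.
- Section 1.3.3 classes F with K and L as two-dose panels ("2-dose Day 1, Day 169-Panels F and K-L"). Its serum rows are marked at both Day 85 and Day 197.
- Section 8.1.8.1 fixes the second injection: "For 2-dose Day 1, Day 57 panels, the second vaccination will be administered on Day 57", and "For 2-dose Day 1, Day 169 panels, the second vaccination will be administered on Day 169".
- Section 9.7 uses the panel-specific day: "An interim analysis may be performed on safety and immunogenicity data through at least Day 197 for Panels K and L".
- Section 8.11.4, under Amendment 04, terminates the study and drops immunogenicity serum from the final visit.

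**The concern.** In A, B, I and J, Day 85 falls 28 days after dose 2. In K and L the matching day is Day 197. The one-dose panels also have serum at Day 85, so limiting the Day 85 ratio to two-dose panels makes sense mainly as a comparison after dose 2. For F, K and L that premise fails.

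A programmer who follows Table 10 would produce a Day 85 ratio for F, K and L that describes one dose, in the row meant for two. The same programmer would produce no ratio to placebo for the 24-week regimen after its second dose, although Section 3 asks for one in K and L. The per-protocol rules in Section 9.5.2 do not catch this, because these participants are on schedule at Day 85.

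**Working it through.** **Timing (Sections 1.3.2, 1.3.3 and 8.1.8.1)**
- A, B, I, J: 85 − 57 = 28 days after dose 2.
- F, K, L at Day 85: 169 − 85 = 84 days before dose 2. With the ±3-day windows the range is 166 − 88 = 78 to 172 − 82 = 90 days.
- F, K, L at Day 197: 197 − 169 = 28 days after dose 2.

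**Two-dose participants at Day 85 (Tables 3 and 4)**
- Second dose already given (A, B, I, J): V591 4 + 4 + 20 + 20 = 48; placebo 1 + 1 + 5 + 5 = 12.
- Second dose not yet given (F, K, L): V591 20 + 20 + 20 = 60; placebo 5 + 5 + 5 = 15.
- Share of V591 with one dose only: 60 of 108, or 56%.

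**Is Day 197 planned elsewhere?** Section 9.7 makes it an optional interim analysis. The next row of Table 10 covers every serum time point, but only with within-group means, so it gives no ratio to placebo.

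**How the plan forms groups.** Table 13 is the only precision figure for these ratios, and it is for Day 29.
- Formula: ratio × exp(± t × SD × √(1/n₁ + 1/n₂)), with n₁ + n₂ − 2 degrees of freedom.
- Inputs: 85% of 84 V591 (71) and 85% of 57 placebo (48), taken from Table 12.
- At SD 1.0 and ratio 1.5 this gives 1.04 to 2.17, the printed value. All 12 cells agree within 0.005.
- The 84 is one dose level summed over panels, so Table 13 pools by dose level at Day 29, when everyone has had one dose. No section states the grouping for Day 85.

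**Conditional illustration: dose-level grouping carried over to Day 85**
- 10^5: A 4 + I 20 = 24 boosted, K 20 unboosted. 10^6: B 4 + J 20 = 24 boosted, L 20 unboosted.
- Panel F V591 is a separate row in Table 12 and would join neither group.
- If dose 2 multiplies the titer by r, the pooled group shows r^(24/44). The values of r are assumptions, not figures from the documents.

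| Assumed r | Pooled group shows |
|---|---|
| 2 | 1.46 |
| 4 | 2.13 |
| 8 | 3.11 |

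**Precision at ratio 2.0, SD 1.0, 85% evaluable (same formula, per dose level)**

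| Comparison | V591 vs placebo | 95% CI |
|---|---|---|
| Day 85, all two-dose panels pooled | 44 vs 27 | 1.18–3.40 |
| Day 85, A, B, I, J only | 24 vs 12 | 0.91–4.38 |
| Day 197, K, L placebo | 20 vs 10 | 0.84–4.76 |
| Day 197, adding Panel F placebo | 20 vs 15 | 0.94–4.27 |

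The 24 combines a younger panel (A or B) with an older one (I or J). The Day 29 evaluable fraction of 85% is carried forward as an assumption.

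**The case against.** The strongest reply is that Section 3 already names the panels and days, Section 9.3 defers to it, and the model can estimate a ratio at any time point after vaccination. On that view Table 10 is loose shorthand and Day 197 would still be reported. This stands in part: the comparison is specified as an objective and the model can supply it. But Table 10 is the detailed strategy for these endpoints, it names a different set of panels and days, and nothing says which text prevails.

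A reader might go further and infer that Table 10 pools F, K and L with boosted panels, so that the Day 85 estimate must understate the boost. The documents do not support that as a statement of fact. Vaccination group is never defined by panel, dose level or regimen, and the pooling visible in Table 13 is for Day 29. If groups are panels or regimens, the K and L ratios at Day 85 are valid one-dose ratios and nothing is diluted. Panel F V591 would stay apart even under dose-level grouping. The 15 placebo participants awaiting a second injection add no dilution either, since the placebo is saline.

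Amendment 04 also stands as a limit. With the study ended early, few or no Day 197 samples may exist, and the documents give no count.

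**Conclusion.** The contradiction is established from the text alone: Table 10 disagrees with Section 3 and the synopsis on both panels and days. It assigns F, K and L a Day 85 ratio when all 60 of their V591 participants are scheduled to have had one dose, and it plans no K/L ratio to placebo after dose 2. For Panel F, the lack of a later comparison lies in Section 3 as well as in Table 10.

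Dilution of the boost is a risk that follows from an undefined term, not a stated feature of the plan. Its size rests on two assumptions: dose-level grouping at Day 85, and the chosen true boost.

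Importance is moderate. The endpoint is secondary, Section 9.9.2 describes the study as descriptive without hypotheses, and termination reduces what can be estimated. What remains at stake is whether a one-dose Day 85 result is reported as a two-dose result.

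**What to change.** 1. Replace the time points in the first row of Table 10 with Day 29 (all panels), Day 85 (Panels A, B, I, J) and Day 197 (Panels K, L).
2. State how Panel F is handled, since Section 3 gives it no comparison after Day 29.
3. Define vaccination group by dose level and regimen at each time point, including whether younger and older panels are combined, and state which placebo participants enter each ratio.
4. If Amendment 04 leaves no Day 197 samples, report that comparison as not estimable. Do not present Day 85 data from F, K and L as a two-dose result.

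The cost is one table row, a definition and the matching model code; no new samples are needed. The statistical price is precision: 24 vs 12 per dose level at Day 85 instead of 44 vs 27 if pooled, with the wider intervals shown above. The pooled interval is narrower because it adds participants who have not had the second dose.

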9.6.3 Demographic and Baseline Characteristics

The comparability of the treatment groups for each relevant demographic and baseline characteristic will be assessed by using summary tables. No statistical hypothesis tests will be performed on these characteristics. The number and percentage of participants screened and randomized and the primary reasons for screening failure and discontinuation will be displayed. Demographic variables (e.g., age, race, and gender), baseline characteristics, and prior and concomitant therapies will be summarized by treatment group either by descriptive statistics or categorical tables.

9.7 Interim Analyses

Up to two interim analyses may be performed on safety and immunogenicity data through at least Day 29. In order to trigger the first interim analysis at least 75% of study participants per Panel in at least 6 Panels must have completed their Day 29 visit. In order to trigger the second interim analysis at least 75% of study participants per Panel in at least 10 Panels must have completed their Day 29 visit.

An interim analysis may be performed on safety and immunogenicity data through at least Day 85 for Panels A, B, I, and J. To trigger this interim analysis at least 75% of these Panel's participants must have completed their Day 85 visit. A minimum percentage of participants from other study Panels is not required for this interim analysis, though all available data will be included.

An interim analysis may be performed on safety and immunogenicity data through at least Day 197 for Panels K and L. To trigger this interim analysis at least 75% of these Panel's participants must have completed their Day 197 visit. A minimum percentage of participants from other study Panels is not required for this interim analysis, though all available data will be included.

These interim immunogenicity analyses will include all available nAb PNA and IgG ELISA data.

For this early phase study, an internal statistician, statistical programmer, and modelers assigned to the protocol will be unblinded throughout the duration of the study to facilitate the interim reviews and analyses of the safety and immunogenicity data. Analyses of immunogenicity data may also be conducted at the discretion of the sponsor when data are available.

Results of the interim analysis will be provided to the unblinded siDMC. The siDMC will make a recommendation for further clinical development. Group summaries will be reviewed by the Sponsor's study team. Sponsor's study team (except for the unblinded statistician and programmer) will be blinded to the V591 treatment information at the participant level.

9.8 Multiplicity

No adjustment will be made for multiplicity.

9.9 Sample Size and Power Calculations

9.9.1 Sample Size and Power for Safety Analyses

The probability of observing at least 1 SAE in this study depends on the number of participants vaccinated and the underlying incidence of participants with a SAE in the study population. Calculations below assume that 100% of the randomized participants will be evaluable for safety analyses. There is an 80% chance of observing at least 1 SAE among 228 participants receive a vaccination of V591 if the underlying incidence of a SAE is 0.70%

(1 of every 143 participants receiving the vaccine). There is a 50% chance of observing at least 1 SAE among 228 participants receive a vaccination of V591 if the underlying incidence of a SAE is 0.30% (1 of every 329 participants receiving the vaccine). If no SAEs are observed among the 228 participants receive a vaccination of V591, this study will provide 97.5% confidence that the underlying percentage of participants with a SAE is <1.61% (1 in every 63 participants) in the V591 group.

Table 11 summarizes the percentage point differences between the 2 vaccination groups that could be detected with 80% probability for a variety of hypothetical underlying incidences of an adverse event. These calculations assume 228 participants receive a vaccination of V591 and 57 participants receive placebo and are based on a 2-sided 5% alpha level. The calculations are based on an asymptotic method proposed by Farrington and Manning (1990) [Farrington, C. P. 1990]; no multiplicity adjustments were made.

Table 11 Differences in Incidence of AE Rates between the 2 Vaccination Groups That can be Detected With an ~80% Probability (Assuming 2-sided 5% Alpha Level With 228 Participants in the V591 Group and 57 Participants in the Placebo Group)

Incidence of Adverse Event		Risk Difference
V591 (%)	Placebo (%)	Percentage Points
6.0	0.1	5.9
11.2	2	9.2
16.9	5	11.9
24.9	10	14.9
31.8	15	16.8
38.2	20	18.2
49.9	30	19.9

Incidences presented here are hypothetical and do not represent actual adverse experiences in either group. Based on an asymptotic method [Farrington, C. P. 1990]

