
Interim Analyses
	
Up to two interim analyses may be performed on safety and immunogenicity data through at least Day 29. In order to trigger the first interim analysis at least 75% of study participants per Panel in at least 6 Panels must have completed their Day 29 visit. In order to trigger the second interim analysis at least 75% of study participants per Panel in at least 10 Panels must have completed their Day 29 visit.
 
An interim analysis may be performed on safety and immunogenicity data through at least Day 85 for Panels A, B, I, and J. To trigger this interim analysis at least 75% of these Panel’s participants must have completed their Day 85 visit. A minimum percentage of participants from other study Panels is not required for this interim analysis, though all available data will be included.
 
An interim analysis may be performed on safety and immunogenicity data through at least Day 197 for Panels K and L. To trigger this interim analysis at least 75% of these Panel’s participants must have completed their Day 197 visit. A minimum percentage of participants from other study Panels is not required for this interim analysis, though all available data will be included.
 
These interim immunogenicity analyses will include all available nAb PNA and IgG ELISA data.
 
Results of the interim analysis will be provided to the unblinded siDMC.

Multiplicity
	
No multiplicity adjustment is planned.

Sample Size and Power
	
Safety: Section 9.9.1 provides information about the ability of this study to estimate the incidence of AEs within the V591 group as well as differences between V591 and Placebo.
 
Immunogenicity: This is a descriptive study and there are no hypotheses to be evaluated. This study will randomize approximately a total of 208 participants into 4 different dose-levels of the V591 group and 52 participants into the placebo group. Section 9.9.2 provides information about the expected variability of the GMT ratios given the sample size.

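### Table 11's 80%-detectable adverse-event differences reproduce only with the group sizes reversed; at the stated 228 V591 and 57 placebo the detection probability is 42% to 78%

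*Combined protocol and SAP*

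**What the plan says.** Section 9.9.1 introduces Table 11 as giving the "percentage point differences between the 2 vaccination groups that could be detected with 80% probability". The sizes and error level are explicit: "These calculations assume 228 participants receive a vaccination of V591 and 57 participants receive placebo and are based on a 2-sided 5% alpha level". The method named is the Farrington-Manning asymptotic one, with no multiplicity adjustment and every randomized participant taken as evaluable for safety. The table title repeats 228 for V591 and 57 for placebo.

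The seven rows (V591 % against placebo %) are 6.0/0.1, 11.2/2, 16.9/5, 24.9/10, 31.8/15, 38.2/20 and 49.9/30.

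The SAP summary in Section 9.1 gives other totals: "approximately a total of 208 participants into 4 different dose-levels of the V591 group and 52 participants into the placebo group". Those agree with the 260 participants of the synopsis and with the panel allocations in Tables 3 and 4.

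**The concern.** Recomputing the table from its own stated inputs gives less than 80% in every row, and about half of that in the first. Safety is the primary objective. Section 9.1 sends the reader to Section 9.9.1 for the trial's ability to estimate V591-placebo differences, and Table 11 is where the ability to detect such a difference is quantified.

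The error runs in the favourable direction throughout and is largest where the background incidence is low. A reader who relies on the table could take a comparison that shows no difference as more reassuring than it is.

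**Working it through.** **Inputs.** Sizes of 228 (V591) and 57 (placebo), two-sided alpha of 0.05, the Farrington-Manning method and the seven incidence pairs, all from Section 9.9.1 and Table 11. Planned sizes of 208 and 52, from Section 9.1 and Tables 3 and 4.

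**Formula.** With V591 rate p1 on n1 participants and placebo rate p2 on n2, and a null difference of zero, the method's null variance is the size-weighted pooled one:

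- pooled rate p = (n1·p1 + n2·p2)/(n1 + n2)
- s0 = √[p(1−p)(1/n1 + 1/n2)]
- s1 = √[p1(1−p1)/n1 + p2(1−p2)/n2]
- power = Φ[(p1 − p2 − 1.96·s0)/s1]

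Because p is weighted by group size and s1 depends on which rate goes with which size, exchanging n1 and n2 changes the answer.

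**First row worked (6.0% against 0.1%).**

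- As stated, 228/57: p = 0.0482, s0 = 0.0317, s1 = 0.0163. Power = Φ[(0.059 − 0.0622)/0.0163] = Φ(−0.195) = 42.3%.
- Reversed, 57/228: p = 0.0128, s0 = 0.0167, s1 = 0.0315. Power = Φ[(0.059 − 0.0326)/0.0315] = Φ(0.837) = 79.9%.
- Planned, 208/52: p = 0.0482, s0 = 0.0332, s1 = 0.0170. Power = Φ[(0.059 − 0.0651)/0.0170] = Φ(−0.357) = 36.0%.

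**All rows, power in %.**

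| V591 / placebo, % | Reversed 57/228 | As stated 228/57 | Planned 208/52 |
|---|---|---|---|
| 6.0 / 0.1 | 79.9 | 42.3 | 36.0 |
| 11.2 / 2 | 80.1 | 60.5 | 54.7 |
| 16.9 / 5 | 79.8 | 67.0 | 61.8 |
| 24.9 / 10 | 80.2 | 72.3 | 67.5 |
| 31.8 / 15 | 80.0 | 74.4 | 69.9 |
| 38.2 / 20 | 80.0 | 76.1 | 71.8 |
| 49.9 / 30 | 80.1 | 78.4 | 74.4 |

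**Solving the other way.** Setting power to 80% and solving for the V591 rate:

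| Placebo, % | Table 11 prints | Reversed 57/228 | As stated 228/57 | Planned 208/52 | Difference at 208/52, points |
|---|---|---|---|---|---|
| 0.1 | 6.0 | 6.03 | 9.45 | 10.26 | 10.2 |
| 2 | 11.2 | 11.17 | 13.67 | 14.50 | 12.5 |
| 5 | 16.9 | 16.95 | 18.95 | 19.82 | 14.8 |
| 10 | 24.9 | 24.85 | 26.38 | 27.31 | 17.3 |
| 15 | 31.8 | 31.80 | 32.99 | 33.95 | 18.9 |
| 20 | 38.2 | 38.19 | 39.09 | 40.07 | 20.1 |
| 30 | 49.9 | 49.88 | 50.29 | 51.26 | 21.3 |

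The reversed sizes return every printed rate to within about 0.05 points.

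**Other explanations tried at 228/57.** None gives about 80% across the rows: unpooled variance 82–95%, unweighted pooled 71–79%, null variance only 46–77%, continuity-corrected 19–74%, one-sided 66–87%, exact score test 37–79%, Fisher 20–74%. Reversing the planned sizes (52/208) gives 76–77%, so the match is specific to 57/228.

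**Where 228/57 comes from.** Table 12 reaches 228 and 57 by including a 125-fold dilution group of 20 V591 participants, with 5 more on placebo (228 − 208 = 20; 57 − 52 = 5). That group is not among the 12 panels.

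**The case against.** The strongest reply is that little hangs on this table. No Tier 1 safety events are defined, so no safety test is planned. Section 9.6.1 treats the Tier 2 intervals as descriptive. Section 4.2 justifies the sample size by the size of the safety database and by precision, not by Table 11, and the pausing rules in Section 6.7.1 work on event occurrence and counts. Amendment 04 ends the study on immunogenicity grounds. At common incidences the reversal by itself costs only 2 to 4 points (76–78% in the last two rows). For rare serious events Section 9.9.1 has a separate at-least-one-event calculation that the reversal does not touch. All of this stands. It limits the weight of the point but does not make the printed figures correct.

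Two further cautions also stand:

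- The reversal is inferred from a seven-row numerical match. What needs no inference is that the printed pairs do not follow from the printed inputs.
- The asymptotic formula is itself rough in the first two rows. At 208/52 an exact score calculation gives 80% power at V591 rates of about 8.9% and 13.8%, against 10.3% and 14.5%.

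A reader might infer that the reversal alone brings the detection probability down to 36–74%. It does not: undoing the reversal at the table's own sizes gives 42–78%, and the lower range also needs the change from 228/57 to 208/52. Nor is 36–74% the power of the trial as enrolled. The documents give planned, approximate sizes and no enrolled counts, and Section 8.11.6 lets panels be omitted or made smaller.

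**Conclusion.** Table 11 is wrong as written. At 228/57, two-sided 5% and Farrington-Manning, the listed differences are detectable with probability 42% to 78%, not about 80%. The gap is about 38 points in the first row and under 2 in the last. Moving to the planned 208/52 is a separate correction and gives 36% to 74%.

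This rests on the plan's own assumptions: all randomized participants evaluable, V591 pooled over doses and regimens against pooled placebo, and no multiplicity adjustment. Nothing suggests that participants were to be randomized in the wrong ratio; every allocation statement has V591 as the larger group at 4:1. The defect lies in a descriptive planning table. It should be corrected, but it puts no decision rule, analysis method or participant at risk.

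**What to change.** Recompute Table 11 by the same method with 208 on V591 and 52 on placebo. For placebo incidences of 0.1, 2, 5, 10, 15, 20 and 30%, the V591 incidences detectable with 80% probability become about 10.3, 14.5, 19.8, 27.3, 33.9, 40.1 and 51.3%, that is, differences of about 10.2, 12.5, 14.8, 17.3, 18.9, 20.1 and 21.3 points.

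Reconcile 228/57 with 208/52 throughout Section 9.9: the Table 11 title and text, the serious-adverse-event sentences, the opening of Section 9.9.2, Table 12 with its dilution group, and the intervals in Table 13. With 208 on V591, the serious-event incidences giving an 80% and a 50% chance of at least one event are 1 − 0.2^(1/208) = 0.77% and 1 − 0.5^(1/208) = 0.33%. The upper bound if none is seen is 1 − 0.025^(1/208) = 1.76%.

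An optional footnote can say that the asymptotic formula is rough in the first two rows and give the exact values (about 8.9% and 13.8%). Replacing the figures by exact ones is not required.

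The cost is one replaced table and some consistent numbers. The stated detectability becomes less favourable. Enrolment, conduct and analysis do not change.
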